## List of Abbreviations and Definition of Terms

ADR	adverse drug reaction
AE	adverse event
ACE	angiotensin converting enzyme
ALT	alanine aminotransferase
AST	aspartate aminotransferase
BSA	body surface area
BUN	blood urea nitrogen
CDISC	clinical data interchange standards consortium
CMO	Contract Manufacturing Organisation
CRF	case report form
CRO	contract research organisation
CTCAE	common terminology criteria for adverse events
EU	European Union
GCP	good clinical practice
GGT	gamma-glutamyl transpeptidase
GMP	good manufacturing practice
HbA1c	average blood glucose level
ICH	International Council for Harmonisation of Technical Requirements for Pharmaceuticals for Human Use
IMP	investigational medicinal product
IRB	institutional review board
LDH	lactate dehydrogenase
MedDRA	Medical Dictionary for Regulatory Activities
Overall improvement rate	A 'substantial resolution' of clinical signs or at least 'moderately improved' in the general change in the target lesion
PDE4i	phosphodiesterase 4 inhibitor
PUVA	psoralen plus UVA
RBC	red blood cell
SAE	serious adverse event
SDTM	study data tabulation model
SGOT	serum glutamic oxaloacetic transaminase
SGPT	serum glutamic pyruvic transaminase

Substantial resolution	A clinical score for thickness and scaliness of 0 and a clinical score for redness of 1 or less in the severity of clinical signs of the target lesion
SUSAR	suspected unexpected serious adverse reaction
UVA	ultraviolet light A
UVB	ultraviolet light B
WBC	white blood cell
WHO	World Health Organisation

## 2 Trial Identification

LP0053-1422

The clinical trial protocol will be registered on [clinicaltrials.gov](http://clinicaltrials.gov), jRCT (Japan Registry of Clinical Trials) and JAPIC (Japan Pharmaceutical Information Center).

## 3 Introduction and Rationale

This Phase 3 clinical trial is being conducted as part of the clinical development programme to obtain marketing approval of LEO 90100 foam (a combination of calcipotriol hydrate plus betamethasone dipropionate) in Japan.

### 3.1 Psoriasis

Psoriasis vulgaris is one of the most common chronic skin diseases, with a prevalence generally estimated at between 1 to 3% of the world's population (1, 2). The prevalence of the disease in Japan could be low (3). It is characterised by sharply marginated areas of affected skin which appear thickened, red and scaly. The scalp, elbows, knees, lower back, hands, feet and nails are commonly affected sites. About 80% of affected patients complain of pruritus (4). Psoriasis is a significant problem in everyday life for the affected patients and has a significant impact on their health-related quality of life, an impact that increases with increasing skin involvement (5).

Psoriasis is a dermatological disease which is characterised by an immune inflammatory reaction, proliferation of epidermal keratinocytes and a disorder of differentiation. The psoriatic appearance of the skin is produced by an increased rate of epidermal proliferation with impaired differentiation of keratinocytes resulting in a thickened, undulating epidermis covered by a thickened, parakeratotic stratum corneum (6,7). Activated T-cells (Th17 and Th1) as well as dendritic cells play an important role among immune and inflammatory reactions in psoriasis. Cytokines (IL-23 and IL-12) produced by dendritic cells are involved in T-cell proliferation and differentiation. Also, IL-22 and IL-17 produced by activated Th17 cause epidermal keratinocyte growth as well as abnormal keratinisation. Therefore, the target of psoriasis treatment is epidermal keratinocytes and immune cells, as well as cytokines produced by these cells. The investigational drug in this trial (LEO 90100 foam) contains two active ingredients with different mechanisms of action: a vitamin D3 analogue and a corticosteroid. The vitamin D3 analogue (calcipotriol) is mainly targeted at the epidermal keratinocyte, and the corticosteroid (betamethasone dipropionate) targets immune cells (8).

### Treatment of psoriasis

Psoriasis vulgaris is a chronic disease for which there is currently no cure. Treatment is targeted at reducing the signs of redness, thickness and scaliness, and associated symptoms such as pruritus. Psoriasis treatments can be divided into three main types: topical treatments, phototherapy and systemic treatments. Each has its own advantages and disadvantages, and several treatment options, for example monotherapy and combination therapy, can be considered in medical practice (9-11). Topical treatment is well-recognised as the first-line medication. Phototherapy [Photochemotherapy (PUVA: psoralen combined with a long-wavelength ultraviolet radiation A, UVA) and middle-wavelength ultraviolet radiation B, UVB (narrow-band or broad-band)] and systemic treatments [such as methotrexate (which is out of insurance-reimbursement in Japan), retinoids and ciclosporin] are generally used in extensive, therapy-resistant and socially disabling disease and in the serious forms of erythrodermic and pustular psoriasis (3,12). Among the most recently approved therapies in Japan are the biological agents, which reduce the effect of T-cells inducing psoriasis, either by a direct effect on the T-cells or by inhibition of their secreted cytokines. Currently 7 such biological products (adalimumab, infliximab, ustekinumab, brodalumab, secukinumab, ixekizumab and guselkumab) have been approved in Japan for the treatment of moderate to severe psoriasis.

For the first-line therapy of psoriasis, topical corticosteroids and vitamin D3 analogues (such as calcipotriol, tacalcitol and maxacalcitol) are effective and the two most commonly used therapies for psoriasis vulgaris. Vitamin D3 analogues do not act as quickly and have to be applied for more than six weeks in order that similar efficacy to corticosteroids can be obtained (13).

“Guidelines of care for the management and treatment of psoriasis with topical therapies” in the US (14) refers to the efficacy of the combination therapy of topical corticosteroids and vitamin D3 analogues. It is very common in Japan to apply both topical corticosteroids and vitamin D3 analogues on the same area simultaneously, to make the best clinical use of each drug. The efficacy of the combination therapy of topical corticosteroids and vitamin D3 analogues in patients with psoriasis vulgaris has been reported by a number of clinical trials performed both in and outside Japan (15-21). In addition to the simultaneous application by patients of topical drugs, combined topical drugs prepared by physicians or pharmacists are often provided to patients in medical practice. Ozawa presented the residual ratio of active vitamin D3 and corticosteroid after the mixing of various types of topical corticosteroids and vitamin D3 analogues and indicated that some inappropriate combinations causing degradation of each of the drugs were observed (22). The compatibility of topical vitamin D3 analogues with topical corticosteroids was also investigated in overseas trials and the results showed

calcipotriol had been degraded substantially when it was mixed with some corticosteroids. This indicates that mixing of vitamin D3 analogues and corticosteroids without regard for this incompatibility should be avoided (23). In addition, as regards to combined drugs prepared by physicians or pharmacists, there are concerns about potential risk of contamination in preparation and the lack of established standard regimes.

Moreover, the issue that increasingly attracts attention is that topical treatment becomes a source of stress for psoriasis patients due to the time taken to apply it. The stress caused by topical treatment is an important factor contributing not only to the decrease of the patients' quality of life, but also to the reduction of drug compliance and therefore to the clinical effectiveness.

To reduce the patient's burden of topical treatment and realise a significant improvement over the currently available treatment, it is essential to decrease time and frequency required to apply the treatments (24-26). For these reasons, a stable and pre-fixed product of an appropriately combined topical corticosteroid and vitamin D3 analogue was developed (Dovobet® ointment), and this was approved in 2014 for use in Japan. Also, the gel formulation which contains the same active ingredients at the same concentration as the Dovobet® ointment was approved in February 2018 for use in Japan.

### 3.2 Experience with Investigational Medicinal Product

In October 2015, LEO 90100 foam was approved in the US as the first country for the topical treatment of plaque psoriasis in patients 18 years of age and older. Overall, the product has been approved in 36 countries, hereof the majority in EU. The foam was launched in US and EU in 2016.

LEO 90100 foam contains the same fixed combination of calcipotriol hydrate 52.2 µg/g (equivalent to 50.0 µg/g calcipotriol) plus betamethasone dipropionate 0.643 mg/g as in the ointment and gel formulations that have been marketed for treatment of psoriasis vulgaris for years. Moreover, both active substances (and the combination thereof) are well established topical treatments for psoriasis.

The safety profile from the marketed combination products (ointment, gel and foam) is based on more than 21,000 subjects involved in LEO Pharma A/S sponsored clinical trials as well as extensive postmarketing experience.

For the ointment and gel formulations, various skin reactions have been reported. The following common and uncommon adverse drug reactions (ADRs) have been reported: pruritus, skin exfoliation, folliculitis, skin infection, skin atrophy, exacerbation of psoriasis,

dermatitis, erythema, rash, purpura or ecchymosis, skin burning sensation, skin irritation, application site pigmentation changes, application site pain, eye irritation, acne and dry skin.

The most frequently reported adverse events (AEs) related to LEO 90100 foam in trials conducted outside Japan were application site reactions. Also, the following uncommon ADRs have been reported: folliculitis, hypersensitivity, hypercalcaemia, skin hypopigmentation, rebound effect, application site pruritus and application site irritation (Investigator's Brochure section 4.8).

The toxicological profiles of calcipotriol and betamethasone dipropionate are well characterised and as expected for the respective drug classes (i.e. vitamin D3 analogue and corticosteroid).

For Dovobet® ointment, no differences in the safety profile have been observed in Japan during the clinical development programme and postmarketing surveillance compared to overseas.

There has been one trial completed so far with LEO 90100 foam in Japanese subjects (27). Twenty healthy Japanese male adults received LEO 90100 foam and its vehicle as each single application on two sites on their back and the skin irritation and photo irritation were evaluated. As a result, only one AE occurred in one subject in the LEO 90100 foam skin irritation test site, which was assessed as 'only slight erythema' on Day 4. No other safety issues related to LEO 90100 foam or vehicle of LEO 90100 foam were reported. Thus, the results indicate safety of LEO 90100 foam in healthy Japanese male subjects.

### 3.3 Trial Rationale

As described above, Dovobet® ointment was approved in Japan in 2014 for the treatment of psoriasis vulgaris. Medicated ointments are generally considered to be the most effective type of formulation for the treatment of inflammatory skin disease with dry or scaly skin such as psoriasis. However, patients may consider ointment formulations greasy, messy and time consuming to apply which often results in poor adherence to therapy and a poor treatment outcome.

To meet patient preferences, a foam formulation of Dovobet® (called LEO 90100 foam) was developed. The formulation is expected to be more convenient and less time consuming to apply than an ointment formulation and is therefore expected to have an improved compliance.

The LEO 90100 foam contains the same strength of active pharmaceutical ingredients and excipients as the Dovobet® ointment dissolved in a mixture of the propellants butane and dimethyl ether. The propellants evaporate immediately after application. The foam provides a novel solution for easy and convenient application of topical treatment for psoriasis.

To obtain approval of LEO 90100 foam for treatment of psoriasis in Japan, a clinical development programme is being conducted in Japan and this trial is part of that programme.

This trial will be performed as an open trial because the trial medications are different formulations, and a double-dummy design would be difficult on a practical basis. The trial design and endpoints are similar to those of a similar trial performed in Japan to compare different topical formulations of the same active ingredient (28). In addition to the target lesion, subjects will be instructed to treat any other psoriasis lesions they may have with the trial medication, apart from those on the scalp, face, genitals and skin folds, providing that all lesions are limited to a total area of less than or equal to 30% body surface area (BSA). This is for the convenience of the subjects, as they do not have to use a different medication on lesions other than the target lesion, and to prevent possible accidental use of this different medication on the target lesion which could impact both the efficacy and safety assessments. When the clinical trial for Dovobet® ointment, comparator of this trial, was conducted, scalp was excluded from the application and the evaluation, and Dovobet® ointment was approved based on the data.

Subjects will be provided with 60g of medication per week. Approximately 20.2g of ointment covers the whole body (29). Hence, approximately 6.1g of ointment covers 30% BSA, the maximum area to which medication can be applied in this trial. This is equal to 42.7g per week as the maximum once daily dosage of ointment. Since LEO 90100 foam has the same composition as Dovobet® ointment, with the exception of the propellants, it should be able to cover at least the same area as the ointment. Therefore, 60g per week should be an adequate amount of medication to provide to the subjects.

### 3.4 Ethical Consideration Statement

The purpose of this trial is to compare LEO 90100 foam and Dovobet® ointment in the treatment of psoriasis in Japanese subjects. The data obtained from this trial will contribute to the development of LEO 90100 foam, a therapy expected to be a useful treatment for psoriasis in the Japanese population.

Even though LEO 90100 foam is a different formulation of the approved product Dovobet® ointment, it contains the same active ingredients at the same concentration and is therefore expected to have a similar safety and efficacy profile. The results of the clinical trials

conducted with Dovobet® ointment in Japan were similar to the results of the clinical trials conducted overseas. Postmarketing surveillance has not revealed any signals indicating a difference between Japanese subjects and non-Japanese subjects.

Subjects participating in the trial will be under the careful supervision of an experienced dermatologist during the entire course of the trial.

Considering the above, this trial is assumed to involve a minimal risk to the participating subjects.

## **4 Trial Objectives**

### **4.1 Primary Objective**

To compare the efficacy of LEO 90100 foam with Dovobet® ointment in the treatment of psoriasis in Japanese subjects.

### **4.2 Secondary Objectives**

To compare the safety of LEO 90100 foam with Dovobet® ointment in the treatment of psoriasis in Japanese subjects.

### **4.3 Exploratory Objectives**

To investigate the subjects' own assessments of the use of LEO 90100 foam compared to previous psoriasis treatments for non-naïve subjects.

## **5 Trial Endpoints**

### **5.1 Primary Endpoint**

The primary endpoint is 'overall improvement rate' for the target lesion at Visit 4 (end of Week 4), defined as 'substantial resolution' of clinical signs or at least 'moderately improved' in the general change in the target lesion. 'Substantial resolution' is defined as a clinical score for thickness and scaliness of 0 and a clinical score for redness of 1 or less in the severity of clinical signs of the target lesion.

### **5.2 Secondary Endpoints**

The 'overall improvement rate' for the target lesion at Visits 2 and 3 (end of Weeks 1 and 2).

The change in the total sign score from Visit 1 to Visit 4; total sign score is defined as the sum of the scores from the 3 clinical signs assessing severity in the target lesion.

The change in the sum of the scores (total sign score) for the severity of the three clinical signs (thickness, scaliness, redness) from Visit 1 to the sum of the scores at Visit 4 (end of Week 4) for the target lesion.

The number of adverse events.

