### Treatment period

The treatment period will last for up to 4 weeks. Trial visits will be performed on Day 1 (Visit 1) and after 1, 2 and 4 weeks (Visits 2, 3 and 4). Visit 2 and Visit 3 should be performed within  $\pm 1$  day of the scheduled time (Day 7-9 and Day 14-16, respectively), and Visit 4 should be performed within  $\pm 2$  days of the scheduled time (Day 27-31), in all cases relative to Visit 1. If they are outside this window, the (sub)investigator should record the reason in the patient's medical record.

At Visit 1, subjects will be randomised to receive treatment with either LEO 90100 foam or Dovobet® ointment. Trial medication will be applied once daily to psoriasis on a target lesion of the body. After this application on the target lesion, subjects will also apply trial medication to any other areas of psoriasis, excluding psoriasis on the scalp, face, genitals, and skin folds (axillae, groin, infra-mammary, those around the buttocks and the perianal area).

On the assessment day of the target lesion (Visit 1, Visit 2, Visit 3 and Visit 4), subject should not apply any topical treatment including emollients on the target lesion before the visit. Showering or bathing should also be avoided.

Subjects with the target lesion achieving 'substantial resolution', as defined in section 5, before the end of 4 weeks' treatment will complete the trial at this time (although they will still be required to attend the follow-up visit up to 14 days later, if applicable; see below).

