## 8.6 Laboratory Assessments

A total of 4.5 mL of venous blood and a urine sample will be taken at the Screening Visit, Visit 1 and at Visit 4, hence 13.5 mL of blood in total for the trial. If a subject withdraws from or completes the trial at Visits 2 or 3, samples should be taken at this time in lieu of the Visit 4 samples. The samples will be analysed for the following parameters:

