### 9.1 Collection of Adverse Events

AEs must be collected from the signing of the informed consent form until the last trial visit.

AEs must be assessed by (sub) investigators who are medically qualified.

At all visits, the (sub)investigator should ask the subject a non-leading question to the effect of: "How have you felt since I saw you last?" No specific symptoms should be asked for. It is important that the (sub)investigator also observes the subject for any changes not reported by the subject and records these changes.

If there are no AEs to record, no further questions should be asked and “NO” should be ticked in the eCRF. In case there are one or more AEs to record, “YES” should be ticked.

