#### **11.3.8.1 Adverse Events**

AEs will be coded during the course of the trial according to MedDRA. AEs will be presented by preferred terms and primary system organ class.

Only treatment emergent AEs will be tabulated but all AEs recorded during the course of the trial will be included in the subject data listings. An event will be considered emergent with the trial treatment if started after the first application of IMP or if started before the first

application of IMP and worsened in severity thereafter. In each of the tabulations, AEs are defined by MedDRA preferred terms within primary system organ class.

An overall summary of AEs and number (percentage) of subjects with any AEs, SAEs, premature discontinuations from the trial due to AEs, treatment related AEs and AEs stratified by severity will be presented.

The number of AEs and number (percentage) of subjects for each type of AE will be tabulated by treatment group. A similar tabulation will be made for AEs stratified by severity.

The causal relationship to trial medication for each type of AEs will be tabulated by treatment group. Where there are several recordings of causal relationship to the IMP for a given type of AE for a subject, causal relationship will be taken as the most-related recording from the last report of that AE, since that is when the (sub)investigator will be in possession of most information and so best able to judge causal relationship.

Related AEs are defined as AEs for which the (sub)investigator has not described the causal relationship to IMP as 'not related'. The number of subjects experiencing each type of related AE will be tabulated regardless of the number of times each related AE is reported by each subject.

Cutaneous AEs will be tabulated, similarly stratified as 'lesional/perilesional' or 'distant'.

SAEs will be evaluated separately and a narrative for each will be given.

AEs leading to withdrawal from trial or discontinuation of IMP will be listed.

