6.7.1 Exposure

In addition to what is stated in the CTP (section 11.3.3), the number of days of exposure will be calculated as the date of final application minus the date of first application plus 1,

ignoring any interim missing applications. The duration of exposure to treatment (weeks) will be derived as the number of days of exposure divided by 7, and will be summarized for each treatment group using the mean, SD, median, minimum and maximum values. The sum of duration of exposures to treatment will be presented as all subjects-treatment-weeks.

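### Adverse-event observation time depends on response, yet the safety endpoint and AE tables carry no time-based rate; add one as a supplement

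*Protocol*

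**What the plan says.** The secondary objective (Protocol 4.2) is comparative: "To compare the safety of LEO 90100 foam with Dovobet" ointment. The matching endpoint in Protocol 5.2 is "The number of adverse events", with no time element.

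Protocol 6.1 (Treatment period) says that a subject whose target lesion reaches substantial resolution before four weeks "will complete the trial at this time (although they will still be required to attend" a follow-up visit where one applies. Protocol 8.6 shows when this can happen, since it provides for samples "If a subject withdraws from or completes the trial at Visits 2 or 3". Protocol 9.1 sets the collection window: "AEs must be collected from the signing of the informed consent form until the last trial visit". Follow-up after that visit is conditional. Protocol 6.1 (Follow-up period) requires it only for an AE present at the last visit that is serious or judged possibly or probably related.

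For analysis, Protocol 11.3.8.1 says: "The number of AEs and number (percentage) of subjects for each type of AE will be tabulated by treatment group". SAP 6.7.2 adds tables by causality and by location but no rate, and none of the titles of Tables 202-214 in SAP Appendix I mentions one. SAP 6.7.1 summarises exposure in weeks for each treatment group and adds: "The sum of duration of exposures to treatment will be presented as all subjects-treatment-weeks". Neither document links that total to the AE tables.

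**The concern.** A count, or a percentage of subjects, compares two arms fairly when both are watched for about the same time. Here a responder may be watched for one or two weeks and a non-responder for four. If the arms differ in how many subjects clear by Week 1 or Week 2, they also differ in AE observation time. Part of any difference in AE counts would then reflect speed of clearance and not tolerability.

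The percentage of subjects with an AE does not remove the problem, because a subject watched for one week also has less chance of a first event. The conditional follow-up visit does not restore equal observation either, since it is triggered by an AE already present. What is at stake is how the comparison named in the secondary objective is read.

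**Working it through.** There is no plan figure to reproduce: the documents state no AE rate, effect size or margin for safety, and Protocol 6.2 says that the sample size is not power-based.

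**Inputs from the documents**
- Visits 2, 3 and 4 fall on Days 8, 15 and 29, so about 1, 2 and 4 weeks of treatment (Protocol 8.1).
- 90 subjects are randomised per arm (Protocol 6.2).
- 17 of 445 patients (17/445 = 3.8%) had an adverse drug reaction in Japanese ointment and gel studies (Protocol Appendix 2). I use this as a low four-week risk. It covers reactions only, so all AEs would be more frequent.

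**Assumptions**
- Share clearing at Visit 2 (a) and at Visit 3 (b) in each arm. The documents give neither, so I vary both.
- An AE hazard *h* per week that is constant and identical in the two arms.
- A four-week AE risk of 30% as a high value.

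**Formulas**
- Mean exposure = a×1 + b×2 + (1−a−b)×4 = 4 − 3a − 2b weeks.
- *h* = −ln(1 − four-week risk)/4. At 30% this is 0.0892; at 3.8% it is 0.0097.
- Expected AEs per arm = 90 × *h* × mean exposure.
- Share of subjects with an AE = 1 − [a·exp(−h) + b·exp(−2h) + (1−a−b)·exp(−4h)].

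**Results, foam v ointment, 30% four-week risk**

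| Cleared at Visit 2 / Visit 3, foam v ointment | Mean exposure (weeks) | Ratio | Expected AEs | Subjects with AE |
|---|---|---|---|---|
| 0/0% v 0/0% | 4.00 v 4.00 | 1.00 | 32.1 v 32.1 | 30.0 v 30.0% |
| 2/8% v 1/5% | 3.78 v 3.87 | 0.977 | 30.3 v 31.1 | 28.5 v 29.1% |
| 5/15% v 2/8% | 3.55 v 3.78 | 0.939 | 28.5 v 30.3 | 26.9 v 28.5% |
| 10/20% v 3/10% | 3.30 v 3.71 | 0.889 | 26.5 v 29.8 | 25.1 v 28.0% |

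In the last row the gap is 90 × 0.0892 × 0.41 = 3.3 events. Treating the counts as Poisson, its standard error is √(26.5 + 29.8) = 7.5, so the gap is about 0.44 standard errors. At a 3.8% risk the same row gives 2.9 v 3.2 events, a gap of about 0.4. As a stress test beyond this range, 20/40% v 5/15% gives 2.60 v 3.55 weeks (ratio 0.73), 20.9 v 28.5 events and about 1.1 standard errors.

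**With a rate.** Dividing expected AEs by subject-weeks gives 100 × *h* in every row: 8.92 per 100 subject-weeks in both arms at 30%, and 0.97 at 3.8%. Under a constant hazard the artefact disappears.

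**Without a constant hazard.** Suppose instead that all AEs arise in the first week. Early exit at Visit 2 or 3 then removes essentially none, and both arms have, say, 32.1 events. In the last row the rates per 100 subject-weeks are 32.1/297 = 10.8 v 32.1/333.9 = 9.6. The faster-clearing arm now looks about 12% worse (1/0.889) although the counts are equal.

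**The case against.** A reader might infer that the plan will flatter the foam, or that an efficacy difference will pass as a safety difference. The documents do not support either reading. The shift needs a between-arm difference in Week 1-2 clearance, and none is given. Protocol 3.4 expects similar efficacy and safety, because the active ingredients and their concentrations are the same. With equal clearance there is no bias, and if the ointment cleared faster the shift would reverse.

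Nor would unequal exposure be hidden. Exposure is summarised by treatment group (SAP 6.7.1, Table 201), substantial resolution is tabulated by visit (Table E12), and percentages of subjects accompany the counts. A reader could work out a crude rate. No AE test, margin or decision rule is specified, so no error rate is affected.

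The rate also has weaknesses. It relies on a roughly constant hazard, and the exposure defined in SAP 6.7.1 runs from first to final application, which is not the same as the AE collection window.

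All of this stands. It limits the size of the point and rules out making the rate the main basis of the safety statement. It does not remove the response-dependent observation time, which follows from the protocol's own rules. Comparing efficacy is the primary objective, so equal clearance cannot be taken for granted in advance.

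**Conclusion.** The point holds in a limited, conditional form. AE observation time depends on response, and no planned AE summary allows for it. If one arm clears faster in Weeks 1-2, that arm would show 0-11% fewer AEs over the assumed exposure ratios of 1.00 to 0.89. This corresponds to at most about 3 events with 90 subjects per arm at a 30% four-week risk, and under 1 at 3.8%. These figures rest on assumed clearance rates and on equal, constant weekly hazards; early clustering of AEs would make the shift in counts smaller. The consequence is for descriptive interpretation only. It does not show that the planned comparison is biased in either direction.

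**What to change.** - In SAP 6.7.2 and Tables 202-204, add AEs per 100 subject-weeks by treatment group as a supplement to the counts and percentages.
- In SAP 6.7.1 and Table 201, state that subject-treatment-weeks are totalled per arm; the current wording leaves open whether the total is pooled.
- State whether the rate's denominator is treatment time (first to final application) or AE observation time (to the last visit at which AEs are collected). If it is the latter, say how the conditional follow-up visit is handled.
- State that the between-arm safety comparison will be read from counts, percentages and rate together. Note that the rate assumes a roughly constant hazard and can overstate the faster-clearing arm's rate if AEs cluster in the first week.

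The cost is one column in each of three tables and a few sentences. The treatment-time denominator is already derived, an observation-time one needs only visit dates, and no new data or visits are required.
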